6.15.3. Deaths, Other Serious Adverse Events, and Other Notable Adverse Events

By-patient listings of deaths, serious AEs (SAEs), and AEs leading to discontinuation will be provided, respectively. All deaths will be included, regardless of the investigator's or the sponsor's judgment about causality, including:

- any deaths occurring during participation in the study in the database for which data are being presented
- any deaths occurring after a patient leaves (is discontinued from or completed) the study in the database for which data are being presented if:
 - the death is the result of a process initiated during the study, regardless of when it actually occurred, or
 - the death occurs during the Period 4 after discontinuation of study drug.

An SAE is any AE that results in one of the following outcomes: death, life-threatening, initial or prolonged hospitalization, disability or permanent damage, congenital anomaly or birth defect, or any other serious/important medical events.

The following summary tables (including treatment group comparison) will be provided for the safety population for Period 2 and the Open-label Treatment Population for Period 3:

- SAEs by PT

- AEs that lead to treatment discontinuation (including death) by PT

A follow-up emergent serious adverse event (FESAE) is defined as an SAE that first occurred or worsened in severity after the date of Visit 12 (that is, Week 52) or the ETV. The following summary tables will be provided for the follow-up population for the Post-Treatment Follow-up Period (Period 4):

- FESAE by PT
- FEAEs that lead to treatment discontinuation (including death) by PT.

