4.1. Overview of Study Design

Study I1F-MC-RHBQ (RHBQ) is a Phase 3, multicenter, randomized, double-blind, placebo-controlled, parallel-group, outpatient study examining the efficacy and safety of ixekizumab as compared to placebo in patients with moderate-to-severe genital psoriasis. The study consists of 4 periods:

- **Period 1: Screening Period** (Visit 1 and Visit 1A) will assess patient eligibility and start e-diary data collection, occurring approximately 7 to 30 days prior to Period 2 (baseline; Week 0; Visit 2).
- **Period 2: Blinded Treatment Period** will occur from Week 0 (Visit 2) up to Week 12 (Visit 7). Patients will be randomized to ixekizumab or placebo in a 1:1 ratio. Two injections of ixekizumab 80 mg SC (total dose of 160 mg) or 2 injections of placebo SC, respectively, will be given at Week 0 (Visit 2). From Week 2 through Week 10 patients will receive ixekizumab 80 mg Q2W SC or placebo Q2W SC (Section 6.1).
- **Period 3: Open-Label Treatment Period** will occur from Week 12 (Visit 7) up to Week 52 (Visit 12). At Week 12 (Visit 7) 1 injection of ixekizumab 80 mg SC and 1 injection of placebo SC (total dose of ixekizumab 80 mg) will be given to patients who were randomized to ixekizumab in Period 2; and 2 injections of ixekizumab 80 mg SC (total dose of ixekizumab 160 mg) will be given to patients who were randomized to placebo in Period 2. During the remainder of Period 3, patients will receive ixekizumab 80 mg Q4W dosing with an option to step-up to Q2W dosing starting at Week 24 through Week 40 (at Visit 9 [Week 24], Visit 10 [Week 28], or Visit 11 [Week 40]) (Section 6.1). This open-label period will allow evaluation of long-term efficacy and safety of ixekizumab through 1 year (52 weeks).
- **Period 4: Post-Treatment Follow-Up** (Visit 801 through Visit 803) is for safety monitoring after treatment discontinuation for any patient receiving at least 1 dose of investigational product. Once patients complete study treatment or discontinue study treatment early, patients will complete the Post-Treatment Follow-Up (Period 4). For patients who have entered Period 4, psoriasis therapy is allowed, as determined appropriate by the investigator. This period occurs from the last treatment period visit or early termination visit (ETV) up to a minimum of 12 weeks following that visit.

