At Week 12, during the Open-Label Treatment Period (Period 3), all patients will be reassigned to ixekizumab 80 mg Q4W. Patients originally assigned to placebo will receive a blinded ixekizumab starting dose of 160 mg as 2 SC injections. To maintain blinding, patients originally assigned to ixekizumab 80 mg Q2W will receive a blinded ixekizumab 80-mg dose and a placebo dose at Week 12. Dosing may be increased in the Open-Label Treatment Period (Period 3) to ixekizumab 80 mg Q2W, starting at Week 24 through Week 40 (at Visit 9 [Week 24], Visit 10 [Week 28], or Visit 11 [Week 40]), if the patient is eligible to receive additional investigational product (that is, if it is determined by the patient and the investigator that the patient needs additional ixekizumab in order to achieve or maintain satisfactory disease control). All patients who increase dosing to 80 mg Q2W will remain on this dose until completion of the treatment period or early discontinuation. [Table RHBQ.6.1](#) shows the treatment regimens. If patients remain on ixekizumab 80 mg Q4W, their last dose will occur at Week 48. If patients step up to ixekizumab 80 mg Q2W, their last dose will occur at Week 50.

Treatment received during the Blinded Treatment Period (Period 2) will remain blinded to investigators, study site personnel, and patients until all patients have completed Week 52

(Visit 12) or have discontinued from the study (moved into Post-Treatment Follow-Up [Period 4]).

The investigator or his/her designee is responsible for the following:

- explaining the correct use of the investigational product to the patient/patient caregiver
- verifying that instructions are followed properly
- maintaining accurate records of investigational product dispensing, collection, and administration
- returning all unused medication to Lilly or its designee at the end of the study

Patients will be instructed to contact the investigator as soon as possible if he or she has a complaint or problem with the investigational product so that the situation can be assessed.

Further instructions and special considerations for the administration of the investigational product are provided in Sections [6.2.1](#) and [6.6.1](#).

Table RHBQ.6.1. Treatment Regimens

Randomized Treatment Arm	Dose Week 0 (Day 1)	Dose Week 2 to Week 10	Dose Week 12	Dose Week 16 to Week 50 ^a
	Blinded Dosing		Open-Label Dosing	

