9.6.1. Adverse Events

Adverse events are classified based upon the Medical Dictionary for Regulatory Activities (MedDRA). A TEAE is defined as an event that first occurred or worsened in severity after the first dose of study treatment and on or prior to the date of the last visit within the treatment period. Both the date/time of the event and the date/time of the dose (ie, injection) are considered when determining TEAEs. For each TEAE, the severity is recorded according to the patient's or physician's perceived severity of the event (mild, moderate, or severe). A follow-up emergent adverse event (FEAE) is defined as an event that first occurred or worsened in severity after the date of Week 52 (Visit 15) or the ETV. For events that are gender specific, the denominator and computation of the percentage will only include patients from the given gender.

An overall summary of AEs will be provided for each treatment period. TEAEs, SAEs including deaths, AEs that led to investigational product discontinuation, and AEs by maximum severity and relationship to investigational product will be summarized by MedDRA system organ class (SOC) and preferred term (PT). TEAEs will also be summarized by PT sorted by decreasing frequency within SOC for all TEAEs, TEAEs by maximum severity, and TEAEs considered possibly related to investigational product.

FEAEs (all, by maximum severity, and FEAEs possibly related to investigational product by the investigator), SAEs including deaths, AEs that lead to study discontinuation will be summarized by MedDRA SOC and PT or by PT for the Post-Treatment Follow-Up Period (Period 4).

In addition to general safety parameters, safety information on specific topics of special interest will also be presented. Potential AESIs will be identified by a standardized MedDRA query (SMQ) or a Lilly defined MedDRA PT listing. The details of the AESIs will be defined in the SAP.

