6.15.2. Adverse Events

Adverse events (AEs) will be classified based upon the latest version of the MedDRA. Adverse events will be recorded at every study visit. Any untoward condition starting on or after the date of informed consent will be considered an AE. Any pre-existing condition which worsens in severity on or after the date of informed consent will be considered and recorded as an AE on the AE eCRF page from the date of worsening onwards.

A treatment-emergent adverse event (TEAE) is defined as an AE that first occurred or worsened in severity after baseline and on or prior to the date of the last visit within the defined treatment period. Both the date/time of the event and the date/time of the dose (that is, injection) are considered when determining TEAEs. Treatment-emergent AEs will be assigned to the respective study periods in which they are considered treatment-emergent.

The MedDRA lowest level term (LLT) will be used when classifying AEs as treatment-emergent.

- The maximum severity recorded for each LLT prior to the first dose date/time in the treatment period will be used as the pre-treatment severity for that LLT. If an event during the baseline period has missing severity, and the event persists during the treatment period, then it will be considered as treatment-emergent, regardless of the post-baseline level of severity. Events with a missing severity during the treatment period will be considered treatment-emergent.
- Adverse events with a particular LLT will be classified as treatment-emergent if they first start on or after the first dose date/time in the treatment period (i.e., a patient has no pre-existing conditions with that lowest level term), or if the severity is greater than the pre-

treatment severity for that lowest level term. If a partial AE start date/time is present, the date/time will be compared as far as possible to the treatment start date/time in order to determine whether the event is treatment emergent or not. If there is any doubt, the event will be flagged as treatment emergent.

A follow-up emergent adverse event (FEAE) is defined as an event that first occurred or worsened in severity after the date of Visit 12 (that is, Week 52) or the ETV:

- The MedDRA LLT will be used when classifying AEs as follow-up emergent.

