- For AEs that are ongoing at the date of Visit 12 or ETV, the maximum severity recorded for each LLT on or prior to the date of Visit 12 or ETV will be used as the follow-up baseline severity for that LLT.
- If a partial AE start date is present, the date will be compared as far as possible to the date of Visit 12 or ETV in order to determine whether the event is follow-up emergent or not. If there is any doubt, the event will be flagged as follow-up emergent, unless the same event was already counted as treatment-emergent during the treatment during a previous treatment period (Period 2 or Period 3).

Adverse events and TEAEs will be summarized and analyzed for the safety population for the Blinded Treatment Period (Period 2). The comparisons between treatment groups will be conducted using Fisher's exact test.

Adverse events and TEAEs will be summarized for the Open-label Treatment Population for the Open-label Treatment Period (Period 3).

The following will be presented for the Blinded and Open-label Treatment periods respectively:

- An overall summary of AEs including the number and percentage of patients who experienced TEAE, TEAE by maximum severity, death, SAE, TEAE related to study drug, discontinuations from the treatment due to an AE, and TEAEs of special interest
- TEAE by SOC and PT
- TEAE by PT
- TEAEs possibly related to study drug (evaluated by the investigator), by SOC and PT
- TEAE by maximum severity, SOC, and PT.

In addition, the overall summary of AEs will also be presented for the patients who received at least one dose of ixekizumab, during the Combined Treatment Period (Blinded Treatment Period [Period 2] and Open-label Treatment period [Period 3]). The summary table includes the number and percentage of patients who experienced TEAE, TEAE by maximum severity, death, SAE, TEAE related to study drug, discontinuations from the treatment due to an AE, and TEAEs of special interest, during the Combined Treatment Period.

Follow-up emergent adverse events will be summarized for the follow-up population for the Post-Treatment Follow-up Period (Period 4):

- FEAE by PT

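### SAP 6.15.3 tabulates Period 4 events leading to treatment discontinuation, when treatment is already over, and no SAP table gives the events leading to study discontinuation that protocol 9.6.1 requires

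*SAP*

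**What the plan says.** Protocol 9.6.1 names these adverse event summaries for Period 4: FEAEs (all, by maximum severity, and possibly related to investigational product), SAEs including deaths, and events tied to leaving the study. On the last it says that "AEs that lead to study discontinuation will be summarized by MedDRA SOC and PT or by PT for the Post-Treatment Follow-Up Period".

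The SAP delivers Period 4 adverse events in three places:

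- Section 6.15.2 gives one table, FEAEs by preferred term.
- Section 6.15.3 gives follow-up emergent SAEs by preferred term, and "FEAEs that lead to treatment discontinuation (including death) by PT".
- Table RHBQ.6.6 adds Period 4 FEAE tables for the hepatic and cytopenia topics.

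The definition is in SAP 6.15.2: "A follow-up emergent adverse event (FEAE) is defined as an event that first occurred or worsened in severity after the date of Visit 12" or the ETV. On dosing, protocol 6.1 says "If patients remain on ixekizumab 80 mg Q4W, their last dose will occur at Week 48" and "If patients step up to ixekizumab 80 mg Q2W, their last dose will occur at Week 50". Protocol 7.1 has product withheld from patients who stop early; they then complete the ETV and Period 4.

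**The concern.** The SAP's Period 4 discontinuation table is conditioned on an outcome that follow-up events cannot newly produce. The protocol asks about a different outcome, leaving the study, which remains possible during follow-up. Protocol 7.1 treats the two as separate, with a reason and date collected for each.

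Period 4 exists for safety monitoring after ixekizumab. A table that is empty or nearly so could be read in the study report as showing that follow-up adverse events did not drive anyone out, when that question was never put to the data.

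A smaller gap sits beside it. SAP 6.15.2 keeps the severity and relatedness tables for Periods 2 and 3 but not for Period 4, although protocol 9.6.1 names both.

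**Working it through.** The documents give no figure to reproduce. The check is a timeline, followed by a comparison of the promised and planned outputs.

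**Step 1: can an FEAE lead to treatment discontinuation?**

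- Completers who stay on Q4W: the last dose is at Week 48 and the FEAE window opens after Week 52. Gap: 52 − 48 = 4 weeks.
- Completers who step up to Q2W: the last dose is at Week 50. Gap: 52 − 50 = 2 weeks. The nominal Week 50 dose falls on day 50 × 7 = 350. Visit 12 is at day 364 ± 7, so at the earliest day 364 − 7 = 357, which is still after the dose.
- Early stoppers: product is withheld first, then the ETV takes place, and the FEAE window opens after the ETV.

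On each route treatment has ended before the window opens, so an event with onset in Period 4 cannot cause treatment to stop.

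**Step 2: what could still enter the table?**

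- Deaths, because the bullet includes them.
- An event that worsens. The FEAE definition covers worsening as well as first occurrence, and SAP 6.15.2 takes the maximum severity up to Visit 12 or the ETV as the follow-up baseline for events ongoing at that date. A non-fatal event that stopped treatment, was ongoing at the ETV and then became more severe would be an FEAE, and it would also be an event that led to treatment discontinuation. That discontinuation happened in Period 2 or 3, and the corresponding tables in 6.15.3 already cover it.

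The table is therefore near-empty, not strictly empty, and a non-fatal entry would add no new discontinuation.

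**Step 3: promised against planned.**

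| Protocol 9.6.1, Period 4 | SAP |
|---|---|
| All FEAEs | FEAE by preferred term (6.15.2) |
| FEAEs by maximum severity | No table |
| FEAEs possibly related | No table |
| SAEs including deaths | Follow-up emergent SAEs by preferred term (6.15.3), taken here as meeting the commitment |
| AEs leading to study discontinuation | Replaced by FEAEs leading to treatment discontinuation (6.15.3) |

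**Step 4: is the study-discontinuation summary supplied elsewhere?**

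- SAP 6.5 summarizes and lists reasons for discontinuation from treatment and from the study, and names the Post-Treatment Follow-up population. This counts withdrawals by reason, not by preferred term.
- SAP 6.15.3 plans a by-patient listing of adverse events leading to discontinuation, without saying which kind, and 6.15.2 plans a listing of all adverse events. Neither is a summary.

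No SAP table supplies the protocol's summary.

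**The case against.** The best case for leaving the SAP alone has three parts.

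First, little information is lost. Withdrawals from follow-up because of an adverse event are counted by reason in disposition. Every severe or related follow-up event is counted in FEAE by preferred term, serious ones again in the follow-up emergent SAE table, and individual cases are in the listings. This stands. A reader might infer that such events would go untabulated or disappear, and the documents do not support that. What is missing is one summary by preferred term and two breakdowns.

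Second, a reader might infer that the SAP table can never hold a non-fatal entry. The worsening clause in the FEAE definition rules that reading out, as Step 2 shows. It does not rescue the table, because such an entry reports a discontinuation from an earlier period.

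Third, protocol 9.2 leaves complete analysis details to the SAP, and asks for an amendment only when a principal feature changes. Severity and relatedness splits in a follow-up period with no treatment comparison are hardly a principal feature, so dropping them is permissible. This also stands, but the same section asks that other changes be described and justified in the study report. It does not make a treatment-discontinuation table answer a study-discontinuation question. The bullet closely matches the Period 2 and 3 bullet above it, where the wording makes sense. Carry-over is a plausible explanation, though the documents do not say so.

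**Conclusion.** The point holds as a mismatch between protocol and SAP in descriptive follow-up safety reporting. One promised summary is replaced by a table that no new non-fatal follow-up event can enter, and two promised FEAE breakdowns have no SAP table although the events themselves are counted. The primary analysis, type I error control and the randomized safety comparison in Period 2 are untouched.

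This rests on two assumptions: that dosing ends as protocol 6.1 and 7.1 describe, and that the unqualified listing in SAP 6.15.3 is not meant to stand in for a summary by preferred term. It should be corrected before the follow-up tables are programmed, but it is a modest reporting matter.

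**What to change.** In SAP 6.15.3, replace the Period 4 discontinuation bullet with a table, by preferred term, of all adverse events (death included) that lead to discontinuation from the study during Period 4.

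Swapping treatment for study while keeping the FEAE restriction would not be enough. The protocol's wording covers adverse events in general. An event that began before Week 52 or the ETV, did not worsen, and led the patient to leave during Period 4 is not an FEAE and would be missed.

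In SAP 6.15.2, either add the Period 4 tables of FEAEs by maximum severity and FEAEs possibly related to investigational product, or record that they were dropped and why.

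The cost is one reworded bullet and either two further tables or a short note. Protocol 7.1 collects the reason and date of study discontinuation, 9.6.1 has severity recorded, and 8.2 has relatedness recorded, so no new data should be needed. The case report form is not among the documents, so check that an adverse event given as the reason for leaving the study can be linked to a coded term.

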6.15.3.1. Special Safety Topics including Adverse Events of Special Interest

Safety information on special topics including AEs of special interest (AESI) will be presented by treatment group and by study period. [Table RHBQ.6.6](#) provides the definitions/derivations and analyses methods (including analyses, summaries and by-patient listings) of special safety topics including AESIs.

Potential AESIs will be identified by a standardized MedDRA query (SMQ) or a Lilly-defined MedDRA PT listing. Preferred terms within an SMQ will be classified as broad and narrow. In the Lilly-defined MedDRA PT listings, Lilly has provided the broad and narrow classifications. The Lilly-defined broad terms are for a more sensitive search of potential events of interest and the Lilly-defined narrow terms are for a more specific search. Therefore, the summaries will include the classifications of broad term (same as pooling narrow and broad terms together) and narrow term.

In the event that the listing of terms or analyses changes for a special safety topic, it will be documented in the IXE PSAP which will supersede this document; it will not warrant an amendment to the individual study SAP.

Fisher's exact tests will be used to compare the treatment groups for the safety population during the Blinded Treatment Period (Period 2).

For the Open-label Treatment Period (Period 3) and the Post-Treatment Follow-up Period (Period 4), summaries will be provided using the Open-label Treatment Population and the Post-Treatment Follow-up Population, respectively.

Table RHBQ.6.6. Definitions and Analyses of Special Safety Topics including Adverse Events of Special Interest

Special Safety Topic	Definition / Derivation	Analysis / Summary / Listing
Hepatic	
Hepatic AE analysis will include events that are potentially drug-related hepatic disorders by using the Medical Dictionary for Regulatory Activities (MedDRA) PTs contained in any of the following standardized MedDRA query (SMQ) or sub-SMQ as defined in MedDRA:
 
 • Broad and narrow terms in the Liver related investigations, signs and symptoms (20000008) • Broad and narrow terms in the Cholestasis and jaundice of hepatic origin (20000009) • Broad and narrow terms in the Hepatitis, non-infectious (20000010) • Broad and narrow terms in the Hepatic failure, fibrosis and cirrhosis and other liver damage (20000013) • Narrow terms in the Liver-related coagulation and bleeding disturbances (20000015) 	
Period 2 (Fisher’s exact test): TEAE by PT within SMQ or sub-SMQ, SAE by PT within SMQ or sub-SMQ, AE leading to treatment discontinuation by PT within SMQ or sub-SMQ
 
Period 3 (Summary): TEAE by PT within SMQ or sub-SMQ, SAE by PT within SMQ or sub-SMQ, AE leading to treatment discontinuation by PT within SMQ or sub-SMQ
 
Period 4 (Summary) FEAE by PT within SMQ or sub-SMQ
 
Listing: TEAE

	
Elevations in hepatic laboratory tests (ALT, AST, ALP, total bilirubin) using performing lab reference ranges are defined as:
 
 • Include scheduled visits, unscheduled visits, and repeat measurements. • Alanine aminotransferase (ALT) or aspartate aminotransferase (AST): maximum post-baseline measurement ≥ 3 times ($3\times$), 5 times ($5\times$), 10 times ($10\times$), and 20 times ($20\times$) the performing lab upper limit of normal (ULN) for all patients with a post-baseline value. 
 ○ The analysis of $3\times$ ULN will contain 4 subsets: patients whose non-missing maximum baseline value is $\leq 1\times$ ULN, $>1\times$ ULN to $<3\times$ ULN, $\geq 3\times$ ULN, or missing. ○ The analysis of $5\times$ ULN will contain 5 subsets: patients whose non-missing maximum baseline value is $\leq 1\times$ ULN, $>1\times$ ULN to $<3\times$ ULN, $\geq 3\times$ ULN to $<5\times$ ULN, $\geq 5\times$ ULN, or missing. ○ The analysis of $10\times$ ULN will contain 6 subsets: patients whose non-missing maximum baseline value is $\leq 1\times$ ULN, $>1\times$ ULN to $<3\times$ ULN, $\geq 3\times$ ULN to $<5\times$ 	
Period 2 (Fisher’s exact test): Elevations in hepatic laboratory tests: maximum baseline category to abnormal maximum post-baseline category
 
Period 3 (Summary): Elevations in hepatic laboratory tests: maximum baseline category to abnormal maximum post-baseline category
 
Period 4 (Summary): Elevations in hepatic laboratory tests: maximum baseline category to abnormal maximum post-baseline category

Special Safety Topic	Definition / Derivation	Analysis / Summary / Listing
	
ULN, $\geq 5 \times$ ULN to $< 10 \times$ ULN, $\geq 10 \times$ ULN, or missing.
 
 ○ The analysis of $20 \times$ ULN will contain 7 subsets: patients whose non-missing maximum baseline value is $\leq 1 \times$ ULN, $> 1 \times$ ULN to $< 3 \times$ ULN, $\geq 3 \times$ ULN to $< 5 \times$ ULN, $\geq 5 \times$ ULN to $< 10 \times$ ULN, $\geq 10 \times$ ULN to $< 20 \times$ ULN, $\geq 20 \times$ ULN, or missing. ● The number and percentages of patients with a total bilirubin measurement ≥ 1.5 times ($1.5 \times$), and ≥ 2 times ($2 \times$) the performing lab ULN during the treatment period will be summarized for all patients with a post-baseline value. 
 ○ The analysis of $1.5 \times$ ULN will contain four subsets: patients whose non-missing maximum baseline value is $\leq 1 \times$ ULN, patients whose maximum baseline is $> 1 \times$ ULN but $< 1.5 \times$ ULN, patients whose maximum baseline value is $\geq 1.5 \times$ ULN, and patients whose baseline values are missing. ○ The analysis of $2 \times$ ULN will contain five subsets: patients whose non-missing maximum baseline value is $\leq 1 \times$ ULN, patients whose maximum baseline is $> 1 \times$ ULN but $< 1.5 \times$ ULN, patients whose maximum baseline is $\geq 1.5 \times$ ULN but $< 2 \times$ ULN, patients whose maximum baseline value is $\geq 2 \times$ ULN, and patients whose baseline values are missing. ● ALP: maximum post-baseline measurement > 1.5 times ($1.5 \times$) the performing lab ULN for all patients with a post-baseline value, and divided into 4 subsets: patients whose non-missing maximum baseline value is $\leq 1 \times$ ULN, $> 1 \times$ ULN to $\leq 1.5 \times$ ULN, $> 1.5 \times$ ULN, or missing. 	
	
Shift for ALT, AST, and total bilirubin from maximum baseline to maximum post-baseline will be produced with the requirements using performing lab reference ranges:
 
 ● Include scheduled visits, unscheduled visits, and repeat measurements. ● Use the maximum non-missing value in the baseline period. ● Use the maximum non-missing post-baseline value within each study period. ● Categories are: 
 ○ ALT: $\leq 1 \times$ ULN, > 1 to $< 3 \times$ ULN, ≥ 3 to $< 5 \times$ ULN, ≥ 5 to $< 10 \times$ ULN, ≥ 10 to $< 20 \times$ ULN, and $\geq 20 \times$ ULN ○ AST: $\leq 1 \times$ ULN, > 1 to $< 3 \times$ ULN, ≥ 3 to $< 5 \times$ ULN, ≥ 5 to $< 10 \times$ ULN, $\geq 10 \times$ to $< 20 \times$ ULN and $\geq 20 \times$ ULN ○ Total bilirubin: $\leq 1 \times$ ULN, > 1 to $< 1.5 \times$ ULN, ≥ 1.5 to $< 2 \times$ ULN, $\geq 2 \times$ ULN ○ ALP; $\leq 1 \times$ ULN, > 1 to $\leq 1.5 \times$ ULN, $> 1.5 \times$ ULN. ● With additional categories: 	
Period 2 (Summary): Shifts from maximum baseline to maximum post-baseline category
 
Period 3 (Summary): Shifts from maximum baseline to maximum post-baseline category

Special Safety Topic	Definition / Derivation	Analysis / Summary / Listing
	
 ○ Decreased: post-baseline category < baseline category ○ Increased: post-baseline category > baseline category ○ Same: post-baseline category = baseline category 	
	
Elevated hepatic criteria: maximum ALT $\geq 3 \times$ ULN and maximum total bilirubin $\geq 2 \times$ ULN, using performing lab reference ranges.
 
Listing of patients who meet any of the following criteria:
 
 • Elevated hepatic criteria: defined as maximum ALT $\geq 3 \times$ ULN, and maximum total bilirubin $\geq 2 \times$ ULN • An ALT or AST $\geq 3 \times$ ULN • An alkaline phosphatase (ALP) $\geq 2 \times$ ULN • A total bilirubin $\geq 2 \times$ ULN 
The listing will include: patient demographics, concomitant medications, ALT/AST/ALP/total bilirubin/GGT by visit, treatment start and stop dates, and reason for treatment discontinuation
	
Period 2 (Fisher’s exact test): Elevated hepatic criteria
 
Period 3 (Summary): Elevated hepatic criteria
 
Period 4 (Summary): Elevated hepatic criteria
 
Listing: Elevations in hepatic laboratory tests

	
Evaluation of Drug-Induced Serious Hepatotoxicity (eDISH) plot: use maximum ALT measurement and maximum total bilirubin measurement with patients having at least one post-baseline ALT and total bilirubin, which contributes one point to the plot. The measurements do not need to be taken at the same blood draw.
	
Period 2: eDISH plot
 
Period 3: eDISH plot
 
Period 4: eDISH plot

Cytopenias
	
Cytopenias are defined using the PTs from the following 2 sub-SMQs of the Haematopoietic cytopenias SMQ (20000027) as specified in MedDRA:
 
 • Broad and narrow terms in the Haematopoietic leukopenia (20000030) • Broad and narrow terms in the Haematopoietic thrombocytopenia (20000031) 	
Period 2 (Fisher’s exact test): TEAE by PT within sub-SMQ, SAE by PT within sub-SMQ, AE leading to treatment discontinuation by PT within sub-SMQ
 
Period 3 (Summary) TEAE by PT within sub-SMQ, SAE by PT within sub-SMQ, AE leading to treatment discontinuation by PT within sub-SMQ
 
Period 4 (Summary): FEAE by PT within sub-SMQ

Special Safety Topic	Definition / Derivation	Analysis / Summary / Listing
		
Listing: TEAE

Infections	
Infections are events including infections, serious infections, opportunistic infections, infections that require therapeutic intervention (antibiotics, antivirals, antifungals, etc.), and any events involving reactivation of TB or hepatitis B or hepatitis C. Specifically, infections are defined using all the PTs from the Infections and Infestations System Organ Class (SOC) as specified in MedDRA.
	
Period 2 (Fisher’s exact test): TEAE by PT, TEAE by maximum severity by PT, SAE by PT, AE leading to treatment discontinuation by PT
 
Period 3 (Summary): TEAE by PT, TEAE by maximum severity by PT, SAE by PT, AE leading to treatment discontinuation by PT

	
Anti-infective medications are defined in Appendix 5 of Ixekizumab Program Safety Analysis Plan Version 7 (IXE PSAP V7) including antibiotics, antifungals, antivirals, or antiprotozoals.
 
Listing of patients experiencing a TEAE of infections will be provided including the following additional information: anti-infective medications use (if treated) with medication start/end dates, indication for use, and route; minimum post-baseline value within treatment Period 2 for leukocytes, platelets, lymphocytes, and absolute neutrophils.
	
Listing: TEAE with anti-infective medications.

	
The opportunistic infections (OI) are defined as:
 
 The Lilly specified list is contained in Appendix 11 of the IXE PSAP V7. The narrow terms are considered opportunistic infections. Medical review of broad terms is needed for final determination of patients with OIs. 
Listing of patients experiencing a TEAE of OIs will be provided including the following additional information: source of identification (CRF or Lilly specified list), primary/secondary site of infection, primary/secondary infection type, primary/secondary identified by a laboratory diagnostic test (Yes/No), acquired in a Health care setting (Yes/No).
	
Listing: TEAE of OIs

Special Safety Topic	Definition / Derivation	Analysis / Summary / Listing
	
The duration of each common ($\geq 1\%$ of total ixekizumab) TEAE PT of Infections and Opportunistic Infections is defined as: Duration of treatment-emergent AE Infections (in weeks) = (End date of AE – Start date of AE + 1) / 7. Only TEAEs of infections beginning during treatment Period 2 will be included in the summary. If an AE has not ended by the date of completion of the treatment Period 2, or date of early discontinuation, it will be censored as of that date (last visit within the treatment Period 2, or date of early discontinuation). If a patient has multiple episodes of the same TEAE, the episode with the greatest severity will be used for the duration of event calculation. If a patient has multiple episodes of the same TEAE with the same severity, the episode with the longest duration will be used for the duration of event calculation.
	
Period 2 (Summary): Duration of Common TEAE – Infections Duration of Common TEAE – Opportunistic Infections

Allergic Reactions / Hypersensitivities	
Allergic reactions/hypersensitivity events will be categorized as either anaphylaxis or non-anaphylaxis events (these will refer to events that are not localized to the site of injection) and summarized separately. Medical reviews are needed for final determination of patients with allergic reactions/hypersensitivities.
 
Allergic Reactions/Hypersensitivity Events, Anaphylaxis: Anaphylaxis has been broadly defined as “a serious allergic reaction that is rapid in onset and may cause death” (Sampson et al. 2006). Identification of cases of potential anaphylaxis from the clinical trial data involves two screening criteria, one designed to specifically identify cases (following Criterion 1) based on narrow terms from the MedDRA SMQ for anaphylactic reaction (20000021), and the second to identify possible cases, following Criterion 2 as defined by Sampson et al. (2006).
 
1) Criterion 1 for anaphylaxis is defined by the presence of a TEAE based on the following MedDRA PTs from the anaphylactic reaction SMQ:
 
 • Anaphylactic reaction • Anaphylactic shock • Anaphylactoid reaction • Anaphylactoid shock • Kounis Syndrome • Type 1 hypersensitivity 
2) Criterion 2 for anaphylaxis requires having TEAEs from two or more of four categories
	
Period 2 (Fisher’s exact test): TEAE by PT within Category, TEAE by maximum severity by PT within Category, SAE by PT within Category, AE leading to treatment discontinuation by PT within Category,
 
Period 3 (Summary): TEAE by PT within Category, TEAE by maximum severity by PT within Category, SAE by PT within Category, AE leading to treatment discontinuation by PT within Category,

Special Safety Topic	Definition / Derivation	Analysis / Summary / Listing
	
of AEs as described by Sampson et al. (2006). Occurrence of these events should be nearly coincident; based on recording of events on CRFs. All qualifying events must be within 1 day of study drug injection.
 
The 4 categories to be considered in Criterion 2 are:
 
 • Category A: Involvement of the skin-mucosal tissue • Category B: Respiratory compromise • Category C: Reduced blood pressure or associated symptoms • Category D: Persistent gastrointestinal symptoms 
The specific MedDRA PTs covered by each of these Criterion 2 categories are shown in Appendix 7 of IXE PSAP V7.
 
Summaries of Criterion 2 anaphylactic TEAEs will be provided by the specific combination of categories as follows:
 
 • AB: events based on meeting Category A and Category B (but no other category) • AC: events based on meeting Category A and Category C (but no other category) • AD: events based on meeting Category A and Category D (but no other category) • BC: events based on meeting Category B and Category C (but no other category) • BD: events based on meeting Category B and Category D (but no other category) • CD: events based on meeting Category C and Category D (but no other category) • ABC: events based on meeting Category A, Category B and Category C (but no other category) • ABD: events based on meeting Category A, Category B and Category D (but no other category) • ACD: events based on meeting Category A, Category C and Category D (but no other category) • BCD: events based on meeting Category B, Category C and Category D (but no other category) • ABCD: events based on meeting each of the 4 Criterion 2 categories 
Summaries of treatment-emergent anaphylactic AEs will be provided for patients meeting each of the 2 criteria and for patients who meet either criteria overall. Severity of treatment-emergent Criterion 2 anaphylactic AEs will be based on the maximum severity of the specific events met by the patient. Maximum severity of an (or overall) treatment-emergent
	

Special Safety Topic	Definition / Derivation	Analysis / Summary / Listing
	
anaphylactic AE will be based on the maximum severity within Criterion 1 and/or Criterion 2.
 
Allergic Reactions/Hypersensitivity Events, Non-Anaphylaxis: TEAEs of allergic reaction/hypersensitivity categorized as non-anaphylaxis events are defined by the narrow terms within Hypersensitivity SMQ (20000214) excluding the PTs noted in Appendix 8 of the IXE PSAP V7 and excluding the anaphylactic events as defined above.
 
A by-patient listing will be provided for all patients experiencing TEAE of allergic reactions/hypersensitivities at any time, including status/criterion of anaphylaxis or non-anaphylaxis, and the associated information collected on Allergic / Hypersensitivity Reaction Follow-Up eCRF page if identified by the investigator.
	
Injection Site Reactions	
Injection site reaction is defined using the PTs from the MedDRA HLT of Injection site reactions as specified by MedDRA excluding the following 10 PTs:
 
 1) Embolia cutis medicamentosa 2) Injection site joint discomfort 3) Injection site joint effusion 4) Injection site joint erythema 5) Injection site joint infection 6) Injection site joint inflammation 7) Injection site joint movement impairment 8) Injection site joint pain 9) Injection site joint swelling 10) Injection site joint warmth 
If the AESI trigger CRF form question “Since the last visit did an Injection Site reaction occur?” is answered “Yes”, the Injection Site Reaction follow-up form will be completed. Some additional information in this follow-up form is described in Appendix 4 of the IXE PSAP V7.
	
Listing: TEAE including information collected on Allergic / Hypersensitivity Reaction Follow-Up eCRF page
 
Period 2 (Fisher’s exact test): TEAE by PT within HLT, TEAE by maximum severity by PT within HLT, SAE by PT within HLT, AE leading to treatment discontinuation by PT within HLT
 
TEAE identified by the investigator PT within HLT: by maximum severity, by maximum redness category, by maximum swelling category, by maximum pain category
 
Period 3 (Summary): TEAE by PT within HLT, TEAE by maximum severity by PT within HLT, SAE by PT within HLT, AE leading to treatment discontinuation by PT within HLT

Special Safety Topic	Definition / Derivation	Analysis / Summary / Listing
